Updated consent forms and HIPAA authorization will be uploaded before the start of recruitment. Ads, questionnaires, etc. will be uploaded for review before recruitment begins.

Recruitment will be a joint effort by Stanford University and Woebot Labs. Woebot will communicate the research opportunity through social media channels. The Stanford team will recruit through listservs and contact participants from previous research studies who are interested in future studies. Working with [name] research team at Stanford, the Woebot team will take part in mapping out message development for the intervention and Woebot's IT team will lead the app programming (including build and quality control/de-bugging). Woebot will collect user data via the Woebot app (automatic process), which

Title : Woebot for Substance Use Disorders during COVID-19 (SU sIRB)
Approval Period: 04/30/2022 - 04/30/2023

will be provided to the Stanford team. The Woebot team will participate in disseminating the study findings via publications and presentations. Participants from recruitment channels will go through and eligibility screener and if eligible, will be asked to use the W-SUDS for 8 weeks and answer a couple of questionnaires administered at the beginning and end of the 8 week period. The data from the questionnaires and app usage during the 8-week period will be analyzed to inform the next study. Woebot will rely on Stanford University IRB for review of this study.

The Stanford team will lead the study evaluations including the study measures, data collection (baseline and follow-ups at the 4- and 8- week marks), data analyses, and writing up of study findings for dissemination. Participants will be randomized to condition after completion via the online assessment platform, which has the functionality to allow randomization to one of two webpages. Those randomized to W-SUDs or WL will see a private, study-only Woebot website or the WL website, respectively. Only then will participants randomized to W-SUDs be informed of Woebot in order to avoid contamination. The WL group has no intervention during the 8-week period and the team will monitor for any intervention usage.

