f) Will it be possible to continue the more (most) appropriate therapy for the participant(s) after the conclusion of the study?

Yes

g) Study Endpoint. What are the guidelines or end points by which you can evaluate the different treatments (i.e. study drug, device, procedure) during the study? If one proves to be clearly more effective than another (or others) during the course of a study, will the study be terminated before the

Title : Woebot for Substance Use Disorders during COVID-19 (SU sIRB)
Approval Period: 04/30/2022 - 04/30/2023

projected total participant population has been enrolled? When will the study end if no important differences are detected?

The endpoint will be the 2-month end-of-treatment survey. This will end the study and study staff will do analysis.

3. Background

a) Describe past experimental and/or clinical findings leading to the formulation of the study.

Woebot's app-based platform and user-centered design philosophy makes it an optimal modality for SUDs treatment delivery; it offers immediate, evidence-based tailored support in the patient's peak moment of craving. An RCT demonstrated that Woebot had statistically and clinically significant reductions in depression compared to a control group, along with best in class app-engagement rates (mean=12 interactions in 14 days). Woebot does not currently offer a SUDs program, although 63% of current users expressed interest in said content. Woebot's current, substantial reach as a consumer app, preliminary data indicating its high user engagement plus efficacy to treat a psychological condition, posies it as an ideal platform for a SUDs-focused, tailored, and immediately scalable digital therapeutic.

In the Woebot-SUDs phase 1 (pilot) study, there are 2,450+ screening attempts, indicating interest in a digital therapeutic CA on substance use both nationally and internationally. 260 were screened out solely for not residing in the U.S.

COVID-19 offers a unique opportunity for research to consider outbreak levels and policies in our analyses, and the potential for differential effects of a treatment for reducing substance use problems during an infectious disease outbreak.

b) Describe any animal experimentation and findings leading to the formulation of the study.

N/A

4. Radioisotopes or Radiation Machines

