Participants and Recruitment: N=160 (nationally) will be invited to participate in this study. Recruitment channels may include Woebot Labs' social media avenues (e.g., Facebook, Twitter, LinkedIn, Woebot.io, Nextdoor), Craigslist, Reddit, physical flyers, emailing clinics (with their permission), posting to Stanford Staffers listserv, and advertising to the WELL cohort. Stanford staff may post in other listservs with permission, and contact participants from other studies if those participants have interest in other studies. The team may use Qualtrics panels to recruit. Participants will be entered into the study on a rolling basis. Neither election or declining to participate in the study will impact Woebot users ability to continue using the product as they wish. Inclusion criteria include: all genders aged 18-65 years, access to Woebot on smartphone, be available and committed to engage with app and complete assessments, be willing to provide email address (as this is how assessment incentives will be distributed), and be literate in English (as W-SUDs conversational and video materials will be in English).

Exclusion criteria include: pregnancy (as W-SUDs will not be specifically developed to address the unique needs of this population), history of severe drug/alcohol use, opioid misuse without medication-assisted treatment, and suicide attempt or opioid overdose within the past year. Participants residing outside the U.S. will not be included. Participants who have ever used Woebot will also not be recruited. Use of Woebot (without SUDs program) post randomization, regardless of group assignment, is allowed. Those who elect to participate will be provided with a specific code to enter into Woebot to cue the SUDs specific content.

Randomization: Randomized controlled trial of W-SUDs vs a wait-list control condition (will get access to the SUD program at the end of the study; no intervention during the 8 week period)

This supplemental study proposes to randomize individuals to two conditions (estimating n=80 in each group), W-SUDs or a wait-list control condition, in order to:

- (i) compare between group substance use outcomes at end-of-treatment;
- (ii) assess and analyze comparative impact of Covid-19 in each group;
- (iii) conduct a moderation analysis. Do putative moderators moderate treatment impact upon substance use outcomes?

Primary aim / outcome: Compare between group treatment outcomes.

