Hypothesis: W-SUDs will have significantly improved outcomes compared to the wait-list control group.

Variable of interest: AUDIT/DAST scores across the two groups.

Secondary aim / outcome: Investigate the differential impact of Covid-19 upon psychological functioning across the two groups (one in W-SUDs, the other without intervention).

Purpose: to understand the impact of Covid-19 under a no intervention vs W-SUDs intervention.

Variables of interest: see list below. These variables will be measured at BL, week 4, and end-of-treatment at week 8. Total of 3 surveys.

Exploratory aim / outcome: To investigate putative moderators of treatment on outcome (and/or of treatment engagement).

Variables of interest include:

Mood: depression (PHQ), anxiety (GAD), loneliness, grief

Covid-19 related situational triggers: financial worry, ability to work, essential worker status, safety at home, children at home, degree of closeness to the illness (know someone who is ill, died),

Title : Woebot for Substance Use Disorders during COVID-19 (SU sIRB)
Approval Period: 04/30/2022 - 04/30/2023

Current treatment engagement: level of engagement in other recovery support systems, alliance to Woebot.

Intervention Delivery: W-SUDs will be administered over the course of 8-weeks. Woebot may follow up by email to encourage participants to open the app and check in. The control group will not have access to the W-SUDs program till after completion of their EOT survey at the 8-week mark. Additionally, while the wait-listed group won't have additional surveys (i.e., post app use), we will gather/analyze the info we get from their use of Woebot.

Survey Administration Plan: Qualtrics or REDCap, HIPAA compliant online data center survey administration tools (commonly used by Stanford University), will be utilized to administer the assessment batteries including BL, 4-week, and the EOT questionnaires. During the consent form section, participants will be asked for their email in order to receive study communications including 1) Their signed consent form, 2) Instructions for downloading the Woebot app and using the referral code for the Woebot-SUDs program, and 3) A survey link for follow up assessments. After the baseline is completed, participants will be emailed their signed consent form and instructions. After the 4-week and 8-week phase, participants will receive their survey links via email.

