There will be a brief internet delivered (via Qualtrics or REDCap) screener that will ascertain if individuals who express interest in participating in the study meet inclusion criteria. The screener-battery will include the Drug Abuse Screening Test (DAST-10), CAGE Questions Adapted to Include Drug Use (CAGE-AID), Michigan Alcohol Screening Test (MAST), Psychosis Screening Questionnaire (PSQ), and a few relevant demographic questions (i.e., age, pregnancy status, suicide or overdose within the past year). Those who do not meet criteria will be welcomed to begin using the generic (non-SUD focused) Woebot and the website without restriction but will not be enrolled into the study. In addition, additional substance treatment resources will be provided.

j) Describe how you will be cognizant of other protocols in which participants might be enrolled. Please explain if participants will be enrolled in more than one study.

Consent form will ask whether the participant is currently enrolled in any additional studies.

k) Payment/reimbursement. Explain the amount and schedule of payment or reimbursement, if any, that will be paid for participation in the study. Substantiate that proposed payments are reasonable and commensurate with the expected contributions of participants and that they do not constitute undue

Title : Woebot for Substance Use Disorders during COVID-19 (SU sIRB)
Approval Period: 04/30/2022 - 04/30/2023

pressure on participants to volunteer for the research study. Include provisions for prorating payment. See payment considerations

Supplemental funding pending approval. \$25 for an Amazon gift card per assessment (baseline, 4 week, and 8 week) completed for each of the 160 participants. Total potential amount possible per participant: \$75

l) Costs. Please explain any costs that will be charged to the participant.

There will be no cost to participants.

m) Estimate the probable duration of the entire study. Also estimate the total time per participant for: (i) screening of participant; (ii) active participation in study; (iii) analysis of participant data.

Total duration estimated to be 3.5 years. Content development is ready. Recruitment for about 2 months.

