Woebot for Substance Use Disorders During COVID-19

NCT04460027

October 01, 2021

Statistical Analysis Plan

Paired samples t-tests and chi-square tests compared the groups on baseline variables. EOT survey completion was 84% (152/180) and significantly higher for participants identifying as non-Hispanic white (89%) compared to other racial/ethnic groups (74%) and for participants with a college degree (89%) relative to high school degree (74%) (p-values<.01). Retention also was higher for participants who at baseline reported more pandemic-related mental health effects and lower levels of craving, pain, and pain interference (p-values<.05). Of the 17 treatment participants lost to follow-up, 16 never registered with the W-SUDs app. Fig. 1 shows rates of noncompliance by condition. Two participants randomized to waitlist (2%) downloaded Woebot (not SUD-tailored) from the app store during the study period. Analyses followed the intent-to-treat protocol.

General Linear Models (multivariate models) tested for group differences in changes in the primary outcome and secondary outcomes. The dependent variables were baseline to EOT change scores. The models adjusted for baseline group differences and applied weights to adjust for correlates of study retention. Participant weights were calculated as the inverse of predicted probability values from a logistic regression model predicting EOT retention with race/ethnicity, education, craving, pain intensity, and pandemic-related mental health effects. Pain rating and pain interference were highly correlated ($r = .74$), due to missing data and multicollinearity, the pain rating item was not included. To examine associations among outcomes, bivariate correlations were run for the changes scores. Lastly, survey data were linked to treatment participants' app use metrics and tested for associations.

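### The SAP's retention weights come from one model with no treatment-arm term, so they do not correct for losses that arise differently in the two arms

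*Protocol*

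**What the plan says.** The SAP's second paragraph analyses change from baseline to EOT, so a participant contributes an outcome only by completing the EOT survey. To allow for non-completion, it weights completers by the inverse of their predicted chance of being retained. The predictions come from a single logistic regression on five baseline variables: ethnic group, schooling, craving, pain, and the pandemic's effect on mental health. Neither randomised arm nor any arm-by-covariate term is listed.

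The SAP's first paragraph gives overall completion as 152 of 180 and adds: "Of the 17 treatment participants lost to follow-up, 16 never registered with the W-SUDs app". It gives no completion rate by arm.

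The protocol describes a different position for each arm at the EOT survey. In section 8a, under Intervention Delivery, the treated arm has the programme throughout: "W-SUDs will be administered over the course of 8-weeks". For the wait-list arm the same paragraph says: "The control group will not have access to the W-SUDs program till after completion of their EOT survey at the 8-week mark". Under Randomization, section 8a puts it more loosely: the wait-list arm "will get access to the SUD program at the end of the study; no intervention during the 8 week period". Section 2g adds: "The endpoint will be the 2-month end-of-treatment survey. This will end the study and study staff will do analysis". Payment does not differ by arm; section 8k offers $25 "for an Amazon gift card per assessment (baseline, 4 week, and 8 week) completed for each of the 160 participants".

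**The concern.** One model without an arm term assumes that a given baseline profile has the same chance of completing EOT in either arm. The SAP's own figures make that doubtful. Almost all W-SUDs losses are people who never registered with the app, and the wait-list arm had no W-SUDs app to register with. The EOT survey also precedes access to the programme in one arm only.

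If the characteristics that predict loss differ between arms, the completers differ between arms at EOT although the randomised groups did not. Pooled weights give the same weight to the same profile in both arms, so they cannot remove that difference. The primary comparison would carry it as bias, while the description of the weights suggests that retention has been dealt with.

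**Working it through.** **1. The SAP's own figure.** 152/180 = 84.4%, which agrees with the stated 84%.

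**2. Losses by arm.** Missing overall: 180 − 152 = 28. W-SUDs: 17 (stated). Wait-list: 28 − 17 = 11 (derived, taking loss to follow-up to mean no EOT survey).

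**3. Arm sizes.** These are not given. The protocol planned equal arms of 80, and 180 were enrolled. The SAP reports two wait-list downloads as 2%; 2/n rounds to 2% for n from 81 to 133. I take 90/90 as the working assumption and 81 to 99 on the wait-list as the range.

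| Wait-list / W-SUDs (assumed) | W-SUDs lost | Wait-list lost | Difference | Fisher p |
|---|---|---|---|---|
| 81 / 99 | 17/99 = 17.2% | 11/81 = 13.6% | 3.6 points | 0.54 |
| 90 / 90 | 17/90 = 18.9% | 11/90 = 12.2% | 6.7 points | 0.30 |
| 99 / 81 | 17/81 = 21.0% | 11/99 = 11.1% | 9.9 points | 0.10 |

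At 90/90 the 95% interval for the difference is −3.9 to 17.2 points. Power to detect a gap of that size is about 23%, so the p-value does not show equal retention either.

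**4. Why pooled weights miss it.** Take one yes/no baseline covariate, present in 45 of 90 in each arm. Keep the losses at 17 and 11. The splits below are assumed, for illustration only.

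- *Same pattern in both arms.* W-SUDs loses 12 with the covariate and 5 without; the wait-list loses 8 and 3. Pooled retention is (90 − 20)/90 = 0.778 with and (90 − 8)/90 = 0.911 without. Weighted W-SUDs completers: 33/0.778 = 42.4 with, 40/0.911 = 43.9 without, so 49.15% have the covariate. Wait-list: 37/0.778 = 47.6 and 42/0.911 = 46.1, so 50.79%. Remaining imbalance: 1.64 points.
- *Different pattern by arm.* W-SUDs loses 14 with and 3 without; the wait-list loses 3 and 8. Pooled retention is (90 − 17)/90 = 0.811 with and (90 − 11)/90 = 0.878 without. W-SUDs: 31/0.811 = 38.2 and 42/0.878 = 47.8, so 44.4%. Wait-list: 42/0.811 = 51.8 and 37/0.878 = 42.2, so 55.1%. Remaining imbalance: 10.7 points. Unweighted, it is 42/79 − 31/73 = 53.2% − 42.5% = 10.7 points, so the pooled weights have changed nothing.

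Weights computed within arm restore 45 and 45 in each arm in both cases, and the imbalance is zero. If the covariate shifts the change score by 1 SD, the second pattern biases the arm difference by 0.107 SD.

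**5. Size in general.** Bias in an arm mean = (non-completer minus completer difference) × share missing. With an assumed difference of 0.5 SD at 90/90:

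- same in both arms: 0.5 × (0.189 − 0.122) = 0.03 SD
- W-SUDs only: 0.5 × 0.189 = 0.09 SD
- opposite in the two arms: 0.5 × (0.189 + 0.122) = 0.16 SD

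For scale, the standard error of the unadjusted completer difference is √(1/73 + 1/79) = 0.16 SD.

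**6. Does an arm-specific model work with so few losses?** A simulation at 90/90 used five covariates, similar loss rates and assumed slopes. Pooled weights left a bias of 0.03 to 0.14 SD. An arm main effect removed it when the slopes were equal in both arms. Weights fitted by arm brought it to about 0.01 SD or less, with no higher root mean squared error.

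**The case against.** **Too few events.** Fitting by arm gives 17/5 = 3.4 and 11/5 = 2.2 losses per predictor, against 28/5 = 5.6 pooled. The warning about unstable weights is fair and is why the fix asks for penalisation or truncation. It does not defeat the point, because by-arm weights in the simulation cost nothing in mean squared error.

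**An arm main effect alone does little.** Largely true: it mostly rescales weights within each arm, and suffices only if the predictors act alike in both arms. Hence the interaction terms or separate fits.

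**The outcome model already adjusts.** The SAP adjusts for baseline group differences. If that set included the five retention predictors, much of the measured selection would be handled there. The SAP does not say which variables qualify, so this cannot be relied on. Unmeasured reasons for loss remain under any of these models.

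**The gap may be chance.** It may. The argument rests on the different routes of loss, not on a proven difference in rates.

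**Stronger readings that a reader might infer.** One is that wait-list participants who skipped the survey forfeited the programme. No section says so. The sentence in section 8a can be a timing rule that keeps the outcome ahead of access, and it can be read together with access at the end of the study. Another is that access acted as a reward that drew controls to the survey and produced 17 versus 11. That needs controls to have known of the condition. Section 2a states: "Only then will participants randomized to W-SUDs be informed of Woebot in order to avoid contamination". Section 8a hints that participants learn of a referral code at consent, but the consent pages are not in the text reviewed. The 16 W-SUDs non-registrants explain the gap at least as well. The protocol also describes a population that seeks little treatment, and both arms were paid the same.

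**Conclusion.** The point holds as a limitation of the weighting model. As described, the weights correct for retention only if the five predictors act identically in both arms, and the SAP reports a route of loss that exists in one arm only. Under the assumptions above (90/90, assumed slopes, selection on measured baseline variables) the bias left is 0.03 to 0.14 SD: below one standard error, and not shown to have occurred. Its direction cannot be read from the documents. This is an inexpensive improvement to the analysis, not evidence that the primary result is wrong.

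Separately, the two statements in section 8a about wait-list access leave open what a participant who never completes the EOT survey receives. That is a gap in the text to be reconciled; it is not evidence of forfeiture or of an incentive effect.

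**What to change.** - In the SAP, add randomised arm and arm-by-covariate terms to the retention model, or fit it separately by arm. With only about 17 and 11 losses, use a penalised logistic fit or truncate the weights, and state the rule.
- Report EOT completion by arm with the arm sizes, and the range of the weights in each arm.
- List the baseline variables that the outcome model adjusts for.
- Because unmeasured reasons for loss remain, a short sensitivity analysis with arm-specific shifts for missing outcomes would be a useful addition.
- In protocol section 8a, reconcile the Randomization and Intervention Delivery paragraphs by stating what wait-list participants who skip the EOT survey receive.

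The cost is a reanalysis of data already held and a few sentences of SAP text. The downside is somewhat more variable weights. The protocol's continuing-review form states that enrolment is closed and only data analysis remains, so the analytic change is still usable, whereas a change in how access is released is not.

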13.1 Consent

W-C19 Consent Form

Check if VA related

a) **Describe the informed consent process. Include the following.**

- Who is obtaining consent? (The person obtaining consent must be knowledgeable about the study.)
- When and where will consent be obtained?
- How much time will be devoted to consent discussion?
- Will these periods provide sufficient opportunity for the participant to consider whether or not to participate and sign the written consent?
- What steps are you taking to minimize the possibility of coercion and undue influence?
- If consent relates to children and if you have a reason for only one parent signing, provide that rationale for IRB consideration.

Consent will be received via the mobile application wherever and whenever the participants choose and will

Title : Woebot for Substance Use Disorders during COVID-19 (SU sIRB)
Approval Period: 04/30/2022 - 04/30/2023

take approximately 5 minutes. This will provide sufficient opportunity for the participant to consider whether or not to participate and sign the online consent by mouse, finger, or stylus since there will be no time limit. The online survey platform can obtain electronic signatures. Study staff will not be with the potential participant and there will be no possibility of coercion or undue influence. No children will be recruited.

b) What is the Procedure to assess understanding of the information contained in the consent? How will the information be provided to participants if they do not understand English or if they have a hearing impairment? See HRPP Chapter12.2 for guidance.

Only English speaking participants will be recruited. The consent form will be readable so those with a hearing impairment will still be able to access it.

c) What steps are you taking to determine that potential participants are competent to participate in the decision-making process? If your study may enroll adults who are unable to consent, describe (i) how you will assess the capacity to consent, (ii) what provisions will be taken if the participant regains the capacity to consent,(iii) who will be used as a legally authorized representative, and (iv) what provisions will be made for the assent of the participant.

The consent form will only be accessible to those using a mobile application since that is the investigational device. Participants will only include those competent to consent in the very low risk study.

